**Table 5: Adverse Events of Special Interest Grading Scale** 

| AESI                 | Mild (Grade 1)       | Moderate (Grade 2)     | Severe (Grade 3)     |
|----------------------|----------------------|------------------------|----------------------|
| Diarrhea with a      | 3 loose stools or    | 4-5 loose stools or    | 6 or more loose      |
| positive C diff test | < 400 grams/24 hours | 400 - 800  grams/24    | stools or            |
|                      |                      | hours                  | > 800 grams/24 hours |
|                      |                      |                        | or requires          |
|                      |                      |                        | outpatient IV        |
|                      |                      |                        | hydration            |
| Arrhythmia           | Asymptomatic,        | Symptomatic;           | Symptomatic and      |
|                      | intervention         | medical                | incompletely         |
|                      | not indicated        | intervention indicated | controlled           |

|  | medically, or   |
|--|-----------------|
|  | controlled with |
|  | device          |

## 9.3. Reporting Procedures

#### 9.3.1. Serious Adverse Events

SAEs will be followed until resolution even if this extends beyond the study's reporting period. Resolution of an AE is defined as the return to pretreatment status or stabilization of the condition with the expectation that it will remain chronic.

Any AE that meets a protocol-defined serious criterion must be submitted immediately (within 24 hours of site awareness) on an SAE form to the DMID Pharmacovigilance Group:

### 9.3.2. Regulatory Reporting for Studies Conducted Under DMID-Sponsored IND

Following notification from the investigator, DMID, the Investigational New Drug (IND) sponsor, will report any suspected AE that is both serious and unexpected. DMID will report an AE as a suspected AE only if there is evidence to suggest a causal relationship between the study drug (fosfomycin) and AE. DMID will notify FDA and all participating investigators (i.e., all investigators to whom the sponsor is providing drug under its IND(s) or under any PI's IND(s)) in an IND safety report of potential serious risks from clinical trials or any other source, as soon as possible, but in no case later than 15 calendar days after the sponsor determines that the information qualifies for reporting as specified in 21 CFR Part 312.32. DMID will also notify FDA of any unexpected fatal or life-threatening suspected AE as soon as possible, but in no case later than 7 calendar days after the sponsor's initial receipt of the information. Follow-up information relevant to an IND safety report will be submitted as soon as the information is available. DMID will notify FDA if any halting rules are met. Upon request from FDA, DMID will submit to FDA any additional data, or information that FDA deems necessary, as soon as possible, but in no case later than 15 calendar days after receiving the request.

All SAEs designated as "not related" to study drug will be reported to the FDA at least annually in a summary format.

#### 9.3.3. Reporting of Pregnancy

Fosfomycin, cefixime, and amoxicillin-clavulanate are pregnancy Class B drugs; levofloxacin is a pregnancy Class C drug, and TMP-SMX is a pregnancy Class D drug. Pregnancies that occur during the study will be reported via The Emmes Corporation's IDES on the Pregnancy Report form within 5 days of site awareness.

Efforts will be made to follow all pregnancies occurring during the study through to outcome, as described in the MOP (e.g., delivery, spontaneous abortion, therapeutic abortion, etc.).

# 9.4. Type and Duration of Follow-up of Subjects after Adverse Events

All AEs grade 2 and above will be followed through resolution or stabilization.

Resolution of an AE/SAE/AESI is defined as the return to baseline, grade 1 or less or stabilization of the condition with the expectation that it will remain chronic.

## 9.5. Halting Rules

### Study Halting Rules

If any of the halting rules, as outlined below, is met, further enrollment will be withheld until the DSMB reviews the safety data and provides its recommendations. The continuation of the administration of study drugs (continue the current antibiotic or switch to other one) will be at the PI discretion.

- Any death reported across the pooled study strategies, related to the treatment of fosfomycin.
- If >2 related SAEs in the same high level group term (HLGT) that are observed in subjects who take more than 1 dose of study prescribed fosfomycin, not including *Clostridioides difficile*.
- If ≥5 AESIs are observed across the pooled study strategies (≥5% if more than 100 subjects enrolled)

## 9.6. Safety Oversight

### 9.6.1. Secondary Medical Assessor

Upon DMID MM request, the principal investigator (PI) will identify a physician with relevant expertise, to act as a Secondary Medical Assessor (SMA). The SMA will examine a subject and/or medical records and provide a medical assessment (or second medical opinion) to the PI for the DMID of the safety event in question. The PI will send to the DMID MM, a summary of the event and include the PI and SMA assessments.

#### 9.6.2. Data and Safety Monitoring Board (DSMB)

Safety oversight will be conducted by a DSMB, an independent group of experts that monitors subject safety, conducts a benefit/risk assessment, and advises DMID. DSMB members will be independent of study personnel participating in the trial, should not have scientific, financial, or other COIs related to the trial, and will have appropriate expertise to contribute to the interpretation of data from the trial.

The DSMB will conduct the following meetings:

- Organizational meeting
- Data review meeting for safety
  - Every year

- An Interim analysis for safety and efficacy after at least approximately 40% of subjects have completed the study
- Ad hoc meetings will occur when a halting rule is met, or when DMID or the DSMB chair has immediate concerns regarding observations during the trial
- Final review meeting will occur 6-8 months after the clinical database is locked to review cumulative safety and efficacy data, which will be provided in a standard summary format. The DSMB may be asked to provide recommendations in response to DMID's questions.

The DSMB will operate under the rules of a DMID-approved charter that will be written at the DSMB's organizational meeting. Procedures for DSMB reviews/meetings will be defined in the charter. Reports may include enrollment and demographic information, medical history, concomitant medications, physical assessments, clinical laboratory values, dosing compliance, and solicited and unsolicited AE/AESIs/SAEs. The DSMB will review SAEs on a regular basis and ad hoc during the trial. The DMID Medical Monitor will be responsible for reviewing SAEs in real time.

Additional data may be requested by the DSMB, and interim statistical reports may be generated as deemed necessary and appropriate by DMID. The DSMB may receive data in aggregate and presented by treatment arm. The DSMB may also be provided with expected and observed rates of the expected AEs. The DSMB will review grouped data in the closed session only. As an outcome of each review/meeting, the DSMB will make a recommendation as to the advisability of proceeding with study drug administration, and to continue, modify, or terminate the trial.

## 10. CLINICAL MONITORING

## **10.1.** Site Monitoring Plan

Site monitoring is conducted to ensure that the human subjects' protections, study and laboratory procedures, study intervention administration, and data collection processes are of high quality and meet sponsor, ICH/GCP guidelines, and applicable regulations, and that the trial is conducted in accordance with the protocol, protocol-specific MOP, and applicable sponsor standard operating procedures. DMID, the sponsoring agency, or its designee will conduct sitemonitoring visits as detailed in the clinical monitoring plan.

Site visits will be made at standard intervals as defined by DMID and may be made more frequently as directed by DMID. Monitoring visits will include, but are not limited to, review of regulatory files, accountability records, eCRFs, ICFs, medical and laboratory reports, and protocol and GCP compliance. Site monitors will have access to each site, study personnel, and all study documentation according to the DMID-approved site monitoring plan. Study monitors will meet with site PIs/designees to discuss any problems and actions to be taken, and will document site visit findings and discussions.

## 11. STATISTICAL CONSIDERATIONS

This is a phase IV multicenter, open-label, randomized pragmatic superiority clinical trial comparing two strategies for step-down oral therapy for cUTI. Participants will be followed for up to approximately 28 days.

## 11.1. Study Hypotheses

No particular hypothesis is made regarding the relative efficacy of the two strategies for step-down oral therapy for cUTI. However, a primary goal of the study is to compare the two strategies in terms of success (clinical cure and microbiological cure) at the test of cure visit in order to make one of three statements regarding the results of the trial: 1) Strategy 1 is superior to Strategy 2; 2) Strategy 2 is superior to Strategy 1; or 3) evidence from the trial is insufficient to conclude that either strategy is superior. Thus, the basic null hypothesis of this trial is that the probability of success at TOC is not conditional on the treatment strategy.

## 11.2. Sample Size Considerations

The primary analysis will be performed using the microbiological intent-to-treat (micro-ITT) population, defined as all randomized patients who have a positive baseline bacterial culture of urine (Table 3Table 4). Positive baseline culture is defined as a culture grown from a urine sample collected prior to treatment with study drug that has  $\geq 10^5$  colony forming units (CFU)/mL (50,000 and above is an allowed cut-off provided it is a causative uropathogen) for non-catheter specimens  $\mathbf{OR} \geq 10^4$  CFU/ml for catheter specimens of a single species of bacteria that causes cUTI (Appendix B).

If a subject's baseline culture grows 2 organisms both relevant to cUTI and each in quantities  $\geq$ 50,000 CFU/mL in the urine, then the baseline culture is considered positive. Cultures with 3 organisms or more grown in the urine culture will be considered contaminated unless there is a causative uropathogen that is growing at  $\geq$ 50,000 CFU/ml and the contaminant are  $\leq$ 40,000 CFU/ml.

For subjects with baseline cultures that grow more than one bacterial species in the urine that are not considered contaminated, microbiological success is defined as reduction of each pathogen to  $<10^4$  CFU/mL on non-catheter urine culture OR  $<10^3$  for catheter specimens

Patients will not be excluded from this population based upon events that occurred post-randomization (e.g., loss to follow-up). An assumption of 92% micro-ITT eligibility is made for the sample size calculations. If 634 subjects are enrolled with 1:1 allocation, 291 subjects per arm would be expected to qualify for the micro-ITT population. Assuming a 10% difference in treatment success at TOC, with 80% success for one strategy and 70% success for the other strategy, there will be 80% power to reject the null hypothesis (Section 11.1) using a two sided

ztest (without continuity correction), with a Type I error rate of 5%. These calculations assume an interim analysis after 40% of subjects have completed the study, with Type I error controlled using Lan DeMets with an O'Brien Fleming spending function. The specific success rates of 70% and 80% are based on a 10% clinically significant difference an approximate rate of success consistent with example calculations in the FDA guidance for cUTI studies. Sample size calculations were computed using PASS 2008 software. The calculations do not adjust for dropout, because analysis methods will include subjects that have dropped out early, assuming they meet micro-ITT criteria (Section 11.4).

If true success rates are instead 65% and 75%, there will be 75% power to conclude a difference in the strategies. If true success rates are 80% and 90%, there will be 92% power to conclude a difference.

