## 11.4. Final Analysis Plan

Planned analyses of all primary and secondary endpoints will be described in detail in the SAP to be prepared by the DCC and finalized prior to unblinding of the study data.

The primary analysis will be a superiority analysis of treatment success at TOC by study arm in the micro-ITT analysis population. Multiple imputation will be used in the case of missing values for treatment success at TOC in the micro-ITT population. The test of the null hypothesis of no difference between the strategies for the primary outcome (Section 11.1) will be performed using linear regression, and will include site, pyelonephritis, and number of bacterial species detected in the urine at baseline as covariates. Further details of the analysis, including the multiple imputation model, will be described thoroughly in the SAP. As a secondary analysis, a difference in treatment success at EOT by treatment strategy will be tested in the micro-ITT population, using methods analogous to the primary analysis. Sensitivity analyses will be performed for the primary analysis including a complete case analysis in which subjects are analyzed as randomized without imputation and tipping point analyses.

The safety analysis population will include all subjects receiving at least one dose of study drug. 95% confidence intervals of frequencies of solicited and unsolicited adverse events, SAEs and AESIs will be provided using the Wilson score method.

Frequency and number of solicited adverse events of grade 2 and above will be reported by treatment arm, study day, and severity, and differences between treatment arms in frequency of grade 2 and above severity solicited adverse events after the first dose of study drug will be tested using Fisher Exact Tests. For subjects receiving fosfomycin, frequency and number of each solicited adverse event of grade 2 and above severity occurring any time from date of first dose of fosfomycin in subjects receiving 2 or more doses until 2 days after last dose of fosfomycin will be tabulated.

Frequency and number of SAEs in subjects receiving at least two doses of fosfomycin during the trial will be tabulated.

For subjects receiving fosfomycin, frequency of each unsolicited adverse event of grade 2 and above severity occurring in subjects receiving at least two doses of fosfomycin until 2 days after last dose of fosfomycin will be tabulated overall and by MedDRA® System Organ Class and Preferred Term.

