5. SAMPLE SIZE CONSIDERATIONS

This is a Phase IV multicenter, open-label, randomized pragmatic superiority clinical trial comparing two strategies for step-down oral therapy for cUTI. The basic null hypothesis of this trial is:

H0: The probability of success (clinical cure and microbiological cure) at TOC is not conditional on the treatment strategy.

This hypothesis testing question will result in one of three statements regarding the results of this trial:

1. Strategy 1 is superior to Strategy 2.
2. Strategy 2 is superior to Strategy 1.
3. Evidence from the trial is insufficient to conclude that either strategy is superior.

The primary analysis will use the micro-ITT population, defined as all randomized subjects who have a positive baseline bacterial culture of urine. Subjects will not be excluded from this population based upon events that occurred post-randomization (e.g., loss to follow-up). An assumption of 92% micro-ITT eligibility is made for the sample size calculations. If 634 subjects are enrolled with 1:1 allocation, 291 subjects per arm would be expected to qualify for the micro-ITT population. Assuming a 10% difference in treatment success at TOC, with 80% success for one strategy and 70% success for the other strategy, there will be 80% power to reject the null hypothesis using a two sided ztest (without continuity correction), with a Type I error rate of 5%. These calculations assume an interim analysis after 40% of subjects have completed the study, with Type I error controlled using Lan DeMets with an O'Brien Fleming spending function. The specific success rates of 70% and 80% are based on a 10% clinically significant difference an approximate rate of success consistent with example calculations in the FDA guidance for cUTI studies. Sample size calculations were computed using PASS 2008 software. The calculations do not adjust for dropout, because analysis methods will include subjects that have dropped out early, assuming they meet micro-ITT criteria (Section 6.3.1).

If true success rates are instead 65% and 75%, there will be 75% power to conclude a difference in the strategies. If true success rates are 80% and 90%, there will be 92% power to conclude a difference.

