Allison (2005) [1] showed that this approach can be extended to allow covariates in the model. Hence, Using simulation studies, Allison showed that multiple imputation using linear regression performed well in estimating regression coefficients in different missing data scenarios (MCAR, MAR) even when compared to logistic regression. The added benefit of using the linear regression model is that it directly provides proportion differences along with their 95% CI after applying PROC MIANALYZE to the model fits from the M multiply imputed datasets.

Due to the low sample size at the close of the study, the results of this hypothesis test should be interpreted with care since the required power to conclude a significant difference was not achieved. An estimate of the composite cure and composite cure difference between the two strategies along with its 95% Wald CI (no continuity correction) and p-value will be provided.

Details of multiple imputation methods for efficacy outcomes specific to DMID-15045 are described in Section 8.4.1.

Step 1: A multiple regression model: $Y_i = \beta_0 + \beta_1 X_1 + \beta_2 X_2 + \beta_3 X_3 + \dots + \beta_c X_c + \epsilon_i$, $\epsilon_i \sim N(0, \sigma^2)$ where Y_i represents the indicator for composite cure and X_c are the covariates described in Section 8.4.1 to be used in the multiple imputation model to generate M multiply imputed datasets.

Step 2: A simple linear regression model $Y_i = \beta_0 + \beta_1 trt + \epsilon_i$ will be fit on each of the m multiply imputed datasets. Estimates of composite cure from each of the m models will be given by the β_1 which represent the difference in treatment success between the two strategies.

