8.4. Imputation of Missing Data

8.4.1. Multiple Imputation of Missing Values of Treatment Success at TOC and EOT

Primary and secondary analyses depend on multiple imputation of treatment success at TOC and EOT, respectively. First, a table showing the number and percentage of missing data for each outcome at EOT and TOC will be presented in [Table 18](#). In order to use the MI model to adjust for bias caused by missing data, we assume that data is missing at random (MAR). To test this assumption, we will fit a logistic model for missing data indicator D (1 if missing, 0 if non-missing) adjusting for covariates of the MI model listed below. Parameter estimates, 95% confidence intervals, and p-values from this model will be provided in

Table 19 at TOC and at EOT. If some of these covariates have a significant relationship with the missing data indicator ($p\text{-value} \leq 0.05$), then the MAR assumption is more likely than MCAR.

In case of missing treatment success at TOC or EOT, multiple imputations of missing treatment success at TOC or EOT will be performed independently, and each subject will have their missing endpoints imputed independently of other subjects' imputations using a subject-specific imputation model. The pseudocode shown below details how missing data for treatment success at TOC (or EOT) will be imputed using m multiply imputed datasets from linear models. The following covariates will be considered for the MI model: treatment strategy, site indicators, age, sex, pyelonephritis status, and number of bacterial species. The number of imputed, m , datasets will be chosen based on the average percent of missing data. Default value will be $m=20$ since sample size calculation assumed a 20% drop-out rate. Similar models will be fit for clinical cure and microbiological success.

As a first step to multiple imputation, an ordered list of variables to include in the subject-specific imputation model will be constructed. Ordering is specified so that exact imputation results from final data are prespecified may be replicated in SAS (using seeds described below). The complete ordered list of variables for the imputation models for treatment success, clinical cure, and microbiological success at TOC and EOT is below:

- Treatment Strategy (Strategy 2 is the reference)
- Indicator of subject enrolled at the site with the second most number of subjects enrolled (binary indicator)

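### The stated 80/75/92% power assumes every TOC outcome is observed; imputing drop-outs does not restore it in the SAP analysis, and SAP 8.4.1 contradicts SAP 5 on whether 20% drop-out was allowed for

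*Protocol*

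**What the plan says.** Protocol 11.2 takes 92% micro-ITT eligibility and states: "If 634 subjects are enrolled with 1:1 allocation, 291 subjects per arm would be expected to qualify for the micro-ITT population". On that basis it gives 80% power for 70% vs 80% success at TOC, 75% for 65% vs 75%, and 92% for 80% vs 90%. The test is a two-sided 5% z-test without continuity correction, with one interim look at 40%. It then says: "The calculations do not adjust for dropout, because analysis methods will include subjects that have dropped out early".

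SAP 5 repeats the figures and the sentence, and ends it with "assuming they meet micro-ITT criteria (Section 6.3.1".

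SAP 8.4.1 says of the number of imputations: "Default value will be $m=20$ since sample size calculation assumed a 20% drop-out rate". The number itself is to follow the data ("datasets will be chosen based on the average percent of missing data"), so 20 is only a default.

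On the analysis, SAP 8.4.1 lists the imputation variables: "The following covariates will be considered for the MI model: treatment strategy, site indicators, age, sex, pyelonephritis status, and number of bacterial species". In SAP 8.1.1, Step 2, a regression on treatment alone "will be fit on each of the m multiply imputed datasets". Protocol 11.4 had planned something different, a regression that "will include site, pyelonephritis, and number of bacterial species detected in the urine at baseline as covariates".

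**The concern.** Two statements about the design look wrong.

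First, the word 'because' presents retention of drop-outs in the analysis as the reason no allowance was needed. Retaining a subject by imputation is not the same as observing the outcome. Multiple imputation carries the uncertainty of the missing value into the variance, and power is regained only as far as the imputation model predicts that value. The SAP model contains strategy and baseline variables, with no EOT result or other post-baseline outcome.

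Second, SAP 5 says drop-out was not built into the calculation and SAP 8.4.1 says 20% was. Both describe the same calculation, so one of them is false.

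A reader of SAP 5 would conclude that drop-out cost no power. A reader of SAP 8.4.1 would conclude that it had already been paid for.

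**Working it through.** **Was drop-out in the sample size?** Inputs from Protocol 11.2: 634 enrolled, 1:1 allocation, 92% eligible.

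- Without drop-out: 634 × 0.92 / 2 = 291.6 per arm, which is the stated 291.
- With 20% drop-out: 291.6 × 0.8 = 233.3 per arm.

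The stated number has no drop-out term, so SAP 5 is right about the calculation and SAP 8.4.1 is wrong.

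**Reproducing the stated power.** For a pooled two-sided z-test with n per arm, difference d and mean rate p̄:

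- SE under the null: s0 = √(2 p̄(1 − p̄)/n)
- SE under the alternative: s1 = √((p1(1 − p1) + p2(1 − p2))/n)
- power ≈ Φ((d − 1.96 s0)/s1)

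For 70% vs 80% with n = 291: s0 = √(2 × 0.75 × 0.25/291) = 0.0359 and s1 = √((0.21 + 0.16)/291) = 0.0357. Then (0.10 − 0.0704)/0.0357 = 0.83, giving 79.7%. The other two pairs give 75.1% and 92.4%. All three match the plan. Adding the 40% look with O'Brien-Fleming spending moves them by about 0.1 point.

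**With outcomes missing.** Take n = 291 × (1 − f), with a share f missing at random and equally by arm. The documents give no rate for unknown TOC outcomes, so f is varied.

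| Missing | Observed per arm | 70 vs 80 | 65 vs 75 | 80 vs 90 |
|---|---|---|---|---|
| 0% | 291 | 79.7% | 75.1% | 92.4% |
| 10% | 262 | 75.4% | 70.6% | 89.6% |
| 20% | 233 | 70.4% | 65.5% | 85.8% |

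To keep 291 observed outcomes per arm:

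- 20% missing: 291/0.8 = 364 per arm after rounding up, or 728/0.92 ≈ 792 enrolled.
- 10% missing: 291/0.9 = 324 per arm after rounding up, or 648/0.92 ≈ 705 enrolled.

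**Does the SAP imputation recover the loss?** Let R² be the share of outcome variance explained by the covariates. It is not in the documents, so it is also varied. For imputation followed by a treatment-only model, the variance is inflated by (1 − R²)/(1 − f) + R². At f = 20% and R² = 12% this is 0.88/0.8 + 0.12 = 1.22, and power for 70% vs 80% is 71.4%. With R² of 0, 5, 12 and 20% it is 70.4, 70.8, 71.4 and 72.1%. At f = 10% it is 75.4, 75.6, 75.9 and 76.3%.

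A simulation of the SAP algorithm agrees. It used 291 per arm, no interim look, 20% missing completely at random, 20 imputations by linear regression without rounding, and 2,000 to 3,000 runs (Monte Carlo error about 1 point).

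| Analysis | 70 vs 80 | 65 vs 75 | 80 vs 90 |
|---|---|---|---|
| Nothing missing | 79.4% | 75.1% | 93.2% |
| SAP imputation | 71.5% | 65.9% | 87.8% |
| Complete cases | 70.4% | 65.0% | 87.6% |

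For 70% vs 80%, the standard deviation of the estimated difference across runs was 0.0410 with imputation, 0.0408 with complete cases and 0.0362 with nothing missing. Imputation therefore recovers essentially no precision.

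**The Protocol 11.4 analysis.** With covariates in the analysis model the factor is (1 − R²)/(1 − f). For 70% vs 80% and R² of 0, 5, 10 and 12%, power is 75.4, 77.5, 79.7 and 80.6% at 10% missing, and 70.4, 72.6, 74.9 and 75.8% at 20% missing. The loss is fully offset when R² equals f.

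**The case against.** The best reply is that nothing was hidden. Both documents say openly that no adjustment was made, and it is literally true that early leavers stay in the micro-ITT analysis. The protocol's sentence also refers to its own Section 11.4, where covariate adjustment might make up the loss. The treatment-only model belongs to the SAP as updated after the trial closed, so the conditional figures describe a 634-subject trial that was never run.

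Part of this stands. No loss is claimed for the Protocol 11.4 analysis, since its covariate strength is unknown. Drop-out is also not the same as a missing outcome. Some early leavers are known failures (Protocol 4 and 6.2, SAP 3.3), so for drop-out alone 20% is an upper case. A missing or contaminated TOC culture (SAP 6.3) adds an unknown outcome only in subjects who have not already failed clinically, and SAP 6.3.3 has contaminated-culture exclusions reviewed.

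The rest does not answer the point. Disclosing that no adjustment was made does not make the stated reason valid, and SAP 5 repeats that reason alongside the SAP's own treatment-only method. Protocol 11.3.2 also mentions an assumption of 20% drop-out. That suggests 20% was anticipated, but it is not in the calculation. The provisions in Protocol 5.3.5 and 11.3.2 for review or more enrolment apply only above 20% drop-out and leave the loss below that level untouched.

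**Conclusion.** The point holds, as a minor correction to how the design is reported. The stated 80/75/92% is conditional on complete TOC outcomes. Under the SAP analysis it falls to about 75/71/90% at 10% missing and 70/65/86% at 20% missing, and covariates explaining 12% of the outcome variance would raise these only to 76/71/90% and 71/66/87%. These figures assume outcomes missing at random and equally by arm; the missing rates and covariate strength are assumptions. The contradiction between SAP 5 and SAP 8.4.1 needs no assumption: the arithmetic supports SAP 5.

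No estimate, test or decision changes. The trial stopped at 62 enrolled and 48 micro-ITT subjects, and SAP 5 already reports 12% power and warns against superiority conclusions. That 12% also assumes complete outcomes, but with 24 per arm it moves only from 12.4% to 11.6% at 10% missing and 10.9% at 20%.

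**What to change.** - **SAP 5.** Keep the disclosure that drop-out was not adjusted for. Replace the reason with a conditional statement: the power of 80/75/92% assumes complete TOC outcomes; with outcomes missing at random and equally by arm it is about 75/71/90% at 10% missing and 70/65/86% at 20% missing.
- **SAP 5, same sentence.** Correct the cross-reference. Section 6.3.1 is the ITT population; the micro-ITT criteria are in 6.3.2.
- **SAP 8.4.1.** Say that the default of 20 imputations reflects an anticipated 20% drop-out that was not built into the sample size.

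The cost is two or three sentences in SAP 5 and one in SAP 8.4.1. No analysis, table or protocol text changes. The reported design power becomes conditional and less favourable.
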